### **14.1.1. Primary Analysis**

The primary criterion, time to first recurrence of AF or atrial flutter emergence, will be described using survival curves according to the Kaplan Meier method. Survival curves will be performed by treatment group. The time to first recurrence of AF or atrial flutter emergence will be compared between treatment groups using with the Log rank test.

The distribution of time to first recurrence of AF or atrial flutter emergence will be described by treatment group using Kaplan-Meier methods, reporting Q1, Q3, median, and the 95% confidence interval (CI).

Survival rates (patients still in sinus rhythm) will be described by treatment group at several time points (including 1 week, 1, 2, 3 and 4 months).

Hazard ratios and 95% confidence intervals (based on the Wald test) will be estimated with a Cox regression model. The PHREG procedure in SAS with option TIES=EXACT will be used to fit the Cox proportional hazards model.

### **14.1.2. Supportive Analysis**

The primary analysis will be repeated on the PP set.

### **14.1.3. Additional Analyses**

To take into consideration the sample size reduction, the predictive probability of success with the expected sample size based on observed data, and the conditional power will be provided to support the statistical decision. Different possible true treatment effects will be assumed for the calculations of conditional power (expected clinically relevant difference of 20%, and observed difference).

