### **Sample size**

Assuming an AF recurrence rate of 85% under placebo and 65% under active group, i.e. a clinically relevant difference  $\Delta$  of 20%, a sample size of 64 assessable patients per group is

required, using a log-rank test of survival curves with a 80 % power and a 5 % two-sided significance level. According to the previous assumptions and assuming a rate of not assessable patients of 15%, a minimum of 76 patients have to be randomised per group. Due to low recruitment, it was decided to stop prematurely the study. 135 patients were finally randomised (instead of 152 initially planned).

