## 18. CHANGES SINCE PROTOCOL REDACTION

The following modifications were made to statistical analyses compared to those envisaged in the Version 9 of the protocol dated December 6th, 2016:

- predictive probability of success and conditional power for primary efficacy criterion will be added
- subgroups analyses for primary criterion will be added
- ROC curves for primary criterion exploratory analyses according to DHA will be added
- the secondary criteria analyses repeated on the PP set will not be performed
- the secondary criteria were extended to the flutter detection as the primary efficacy criterion
- VS parameters in standing positions will not be analysed (only provided in individual data listings)
- Frequencies on the ECG clinical interpretation will not be presented (not collected)- Analysis of TEAEs occurrences by MedDRA SOC, PT, seriousness and Treatment Group will be added as per EudraCT requirement

**Note:** the Full Analysis Set definition was clarified with the definition of successful cardioversion as either spontaneous cardioversion before V3 or successful ECV performed at V3.

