11.4.1.1	Time to first recurrence of AF or atrial emergence - KM summary [PP]	11_4_1_2_2_supana_KM.RTF
11.4.1.1	Time to first recurrence of AF or atrial emergence - Cox analysis [PP]	11_4_1_2_3_supana_cox.RTF
	Time to first recurrence of AF or atrial emergence - Survival curves and Logrank test [FAS patients with a DHA baseline <= median of the DHA at baseline]	11_4_1_4_1_sensana_DHA1_KM.gif
	Time to first recurrence of AF or atrial emergence - KM summary [FAS patients with a DHA baseline <= median of the DHA at baseline]	11_4_1_4_2_sensana_DHA1_KM.RTF
	Time to first recurrence of AF or atrial emergence - Cox analysis [FAS patients with a DHA baseline <= median of the DHA at baseline]	11_4_1_4_3_sensana_DHA1_cox.RTF
	Time to first recurrence of AF or atrial emergence - Survival curves and Logrank test [FAS patients with a DHA baseline > median of the DHA at baseline]	11_4_1_4_4_sensana_nonDHA2_KM.gif
	Time to first recurrence of AF or atrial emergence - KM summary [FAS patients with a DHA baseline > median of the DHA at baseline]	11_4_1_4_5_sensana_DHA2_KM.RTF
	Time to first recurrence of AF or atrial emergence - Cox analysis [FAS patients with a DHA baseline > median of the DHA at baseline]	11_4_1_4_6_sensana_DHA2_cox.RTF

SECTION	Title	RTF reference
	Time to first recurrence of AF or atrial emergence - Survival curves and Logrank test [FAS patients with vascular or cardiac therapeutic procedures that will be identified in the data review meeting report<3months]	11_4_1_5_1_sensana_surg1_KM.gif
	Time to first recurrence of AF or atrial emergence - KM summary [FAS patients with vascular or cardiac therapeutic procedures that will be identified in the data review meeting report<3months]	11_4_1_5_2_sensana_surg1_KM.RTF
	Time to first recurrence of AF or atrial emergence - Cox analysis [FAS patients with vascular or cardiac therapeutic procedures that will be identified in the data review meeting report<3months]	11_4_1_5_3_sensana_surg1_cox.RTF
	Time to first recurrence of AF or atrial emergence - Survival curves and Logrank test [FAS patients without vascular or cardiac therapeutic procedures that will be identified in the data review meeting report<3months]	11_4_1_5_4_sensana_surg2_KM.gif
	Time to first recurrence of AF or atrial emergence - KM summary [FAS patients without vascular or cardiac therapeutic procedures that will be identified in the data review meeting report<3months]	11_4_1_5_5_sensana_surg2_KM.RTF

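### Do the predictive probability and conditional power in SAP Section 14.1.3 need a stated target size, a prior and an output row?

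*SAP*

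**What the plan says.** SAP Section 6 (Sample size) assumes recurrence of 85% on placebo and 65% on active, a log-rank test, 80% power and a two-sided 5% level. From these it states "a sample size of 64 assessable patients per group is" required. Allowing for 15% not assessable, it plans 76 randomised per group. It then reports the early stop: "135 patients were finally randomised (instead of 152 initially planned".

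Section 14.1.3 responds to that reduction. It plans "the predictive probability of success with the expected sample size based on observed data". The second quantity follows in the same sentence, with its purpose: "and the conditional power will be provided to support the statistical decision". For conditional power it names two effects, the 20-point design difference and the observed difference. It gives no number for the target size, no event count and no prior.

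Section 18 introduces its list with "The following modifications were made to statistical analyses compared to those envisaged in the Version 9 of the protocol", and that list includes "predictive probability of success and conditional power for primary efficacy criterion will be added". Section 8 reserves causal interpretation for the primary test and treats all other results as exploratory.

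In Appendix 5 the outputs for the primary criterion pass from "11_4_1_2_3_supana_cox.RTF" to "11_4_1_4_1_sensana_DHA1_KM.gif". Nothing is numbered 11_4_1_3, and no title mentions either quantity.

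**The concern.** Predictive probability needs a final sample size (or information fraction), the data so far and a prior. Conditional power needs the same final size and an assumed effect. Section 14.1.3 fixes only the assumed effects. Section 6 offers two possible targets, 152 randomised or 128 assessable, and a log-rank test draws its information from events, for which no target is stated. The protocol is unlikely to fill the gap, because Section 18 presents both quantities as additions to its analyses.

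Section 6 requires the SAP to be signed before the randomisation code is released, so anything left open could be settled after unblinding. The two figures exist to put a shortened trial in context, and Section 14.1.3 ties them to the statistical decision. If the open choices moved them far, the same data could be presented as unlikely, or about as likely as not, to have succeeded at full size. A programmer working only from Appendix 5 might also leave them out.

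**Working it through.** **Inputs from SAP Section 6:** recurrence 85% v 65%, power 80%, two-sided 5%, 64 assessable per group, 15% not assessable, 76 per group (152) planned, 135 randomised.

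**Assumed, because the SAP has no results:** log-rank p = 0.10 (z = 1.645), with p = 0.057 (z = 1.903) as a second case; the alternative loss and recurrence rates; the informative priors.

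**1. Reproduce the design.**
- Under proportional hazards, HR = ln(0.35)/ln(0.15) = 0.553.
- Freedman events = (1.960 + 0.842)² × ((1 + 0.553)/(1 − 0.553))² = 94.9, so 95.
- The mean event rate is (0.85 + 0.65)/2 = 0.75. Then 95/0.75/2 = 63.3, so 64 per group, as stated.
- 64/0.85 = 75.3, so 76 per group and 152 in total, as stated.

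The 128 and the 152 are therefore one design, before and after inflation.

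**2. Formulas.** Let t be the information fraction, b = z√t, and design drift 1.960 + 0.842 = 2.80.
- Conditional power, observed effect: Φ((z/√t − 1.96)/√(1 − t)).
- Conditional power, design effect: Φ((b + 2.80(1 − t) − 1.96)/√(1 − t)).
- Predictive probability: Φ((b + m(1 − t) − 1.96)/√((1 − t) + v(1 − t)²)). A flat prior has v = 1/t and m = b/t. A normal prior with mean θ₀ and SD τ has v = 1/(1/τ² + t) and m = v(θ₀/τ² + b).

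**3. Does the choice of target matter at the SAP's own 15%?** At z = 1.645:

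| Target | t | CP, observed | CP, design | PP, flat |
|---|---|---|---|---|
| 152 randomised | 135/152 = 0.888 | 26% | 39% | 27% |
| 128 assessable, 57 per group available | 114/128 = 0.891 | 26% | 38% | 27% |

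The two readings agree.

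**4. What produces the larger values?** Also at z = 1.645, with a flat prior:
- 20% loss against a fixed 128: t = 108/128 = 0.844, PP 35%.
- 30% loss against a fixed 128: t = 94/128 = 0.734, PP 47%. At 30% loss, 152 randomised would give 152 × 0.70 = 106 assessable. Reaching 128 would take 128/0.70 = 183 randomised.
- 60% recurrence against a target of 96 events (64 × (0.85 + 0.65)): t = 114 × 0.60/96 = 68.4/96 = 0.713, PP 49%. At 60% recurrence, 128 assessable would give 76.8 events. Reaching 96 would take 96/0.60 = 160 assessable, or 160/0.85 = 188 randomised.

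Measured against the planned trial, both extremes disappear. At 30% loss, t = (135 × 0.70)/(152 × 0.70) = 0.888. At 60% recurrence, t = 68.4/76.8 = 0.891. PP is 27% in each case.

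**5. The prior.** At t = 0.888, with τ = 2.80/1.96 = 1.43 and θ₀ = 0 (sceptical) or 2.80 (centred on the design effect):

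| Observed p | Sceptical | Flat | Design-centred |
|---|---|---|---|
| 0.10 | 21% | 27% | 31% |
| 0.057 | 48% | 57% | 60% |

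Conditional power uses no prior.

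**6. Would a fixed event target be better?** The trial has a fixed size and a fixed 20-week follow-up, and Section 14.1.3 speaks of sample size, not events. If all 135 entered the Full Analysis Set (FAS) with the design's mean event rate, there would be 135 × 0.75 = 101 events. Then 101/96 exceeds 1, and nothing would be left to predict.

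**The case for a change.** The strongest case for a change runs as follows. The SAP is the only place where these quantities can be defined, and it leaves the target size and the prior open. The FAS requires a successful cardioversion at visit 3 and counts early relapse as failure, so loss from 135 may well exceed 15%, and a literal target of 128 assessable then departs from 152 randomised. The prior matters even at 15%. The correction would cost only a few lines.

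The textual facts stand: no number, no prior, no output row. The fall from 135 to the FAS is also unknown. But a higher loss would have affected the planned 152 in the same way, so it does not alter the fraction of the planned trial that was completed. Holding 128 fixed while raising the loss asks about a different, larger trial.

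The prior remains a real degree of freedom, though a modest one. Section 14.1.3 bases the calculation on observed data, which points to a flat prior rather than one centred on no effect or on the design effect.

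The Appendix 5 omission is real, but a missing row does not make a value indeterminate, and Section 14.1.3 itself commits to providing both figures. The numbering gap is weak evidence of anything more: 11_4_1_5_1 serves both a procedure subgroup and the country interaction, 11_4_1_2_4_1 serves two different secondary endpoints, and the ROC curves added in Section 18 have no row either.

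**Conclusion.** No change to the plan is needed. The missing detail is of a kind that analysts fill sensibly. The target is the planned size in Section 6, the natural prior is flat, and the 20-point difference becomes HR 0.553 under proportional hazards. On that reading an assumed p of 0.10 gives a predictive probability of 27%, with conditional power of 26% at the observed effect and 39% at the design effect. Choosing 128 assessable instead of 152 randomised changes each by at most about one percentage point at the SAP's 15%. The prior moves the predictive probability over 21% to 31% at p = 0.10 and 48% to 60% at p = 0.057. These figures rest on the assumed p-values and priors and on information accruing in proportion to patients.

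The link to the statistical decision in Section 14.1.3 is loose wording beside Section 8, which leaves that decision to the primary test. The log-rank test, its 5% level, and the hazard ratio with its confidence interval are the same whichever inputs are used. Stating the prior and adding an output row would be tidy, but would change no conclusion of the trial.

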## 8. INFERENTIAL PRINCIPLES

Only the test on the primary criterion, on which is based the sample size justification, may lead to a causal interpretation. All other statistical results are to be regarded as exploratory. Statistical tests will be two-sided and the significance level will be set to 5 %.

In order to obtain statistical modelling convergence and balance number of randomised patients, Poland (with only four randomised patients) will be grouped with the country that randomised the second lowest number of patients (Hungary). Categorical variable “Country” will be analysed with 4 levels for stratified statistical tests and statistical modeling: Italy, Spain, Czech Republic and Hungary.

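### SAP 14.1.3 gives conditional power and predictive probability, computed on the final data, a part in the statistical decision, in tension with Section 8, which makes them exploratory

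*SAP*

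**What the plan says.** Section 14.1.3 (Additional Analyses) responds to the reduced sample size with two calculations. The first is "the predictive probability of success with the expected sample size based on observed data". The second is conditional power under two assumed effects: "expected clinically relevant difference of 20%, and observed difference". It states their purpose: "the conditional power will be provided to support the statistical decision".

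Section 8 (Inferential Principles) sets the rule for inference: "Only the test on the primary criterion, on which is based the sample size justification, may lead to a causal interpretation". It continues: "All other statistical results are to be regarded as exploratory". The level is two-sided 5%.

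Section 6 places the analysis after database lock and code release, and reports that the study stopped early for low recruitment with 135 patients randomised instead of 152. Section 18 lists the calculations as a change from the protocol: "predictive probability of success and conditional power for primary efficacy criterion will be added".

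The SAP does not say which decision is meant. It gives no threshold, prior or information scale for these quantities, and 14.1.3 does not say that they leave the log-rank conclusion untouched.

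**The concern.** Conditional power and predictive probability are normally used at an interim look, to judge whether continuing is worthwhile. Here there is nothing left to continue. At the final analysis each is a monotone function of the log-rank z-value once the information fraction and the assumed effect (or prior) are fixed, so neither adds evidence to the p-value and hazard ratio. The version under the 20-point difference also credits the missing patients with the effect the trial was meant to test.

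Giving such figures a part in the statistical decision leaves room for a near miss to be described as a trial that would probably have succeeded at full size. Whether that description is available depends on a threshold and an information scale that the SAP leaves open.

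**Working it through.** **1. Reproduce the design figure.** Inputs from Section 6, Sample size: recurrence 85% and 65%, 80% power, two-sided 5%, 64 assessable per group, 15% not assessable, 76 randomised per group.

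- HR = ln(0.35)/ln(0.15) = 0.553.
- Freedman events = (1.960 + 0.842)² × ((1 + 0.553)/(1 − 0.553))² = 95 after rounding up.
- Mean event rate = (0.85 + 0.65)/2 = 0.75, so 95/0.75 = 126.7 patients, or 64 per group. This matches.
- 64/0.85 = 75.3, or 76 per group. This matches.

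**2. Cost of the shortfall.** 135 × 0.85 × 0.75 = 86 events give about 76% power by the same method. The planned 152 give 96.9 events and about 81%. The loss is about 5 points.

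**3. Set-up.** Let t be the information fraction, z the final log-rank statistic (positive favours active), c = 1.96, and θ the drift at full information.

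- Conditional power: CP = Φ[(z√t + θ(1 − t) − c)/√(1 − t)].
- Design effect: θ = √96 × (1 − 0.553)/(1 + 0.553) = 2.82, with 96 = 128 × 0.75 events.
- Observed effect: θ = z/√t.
- Flat-prior predictive probability: PP = Φ[(z/√t − c)/√((1 − t)/t)].

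The SAP gives no t. I assume t = 135/152 = 0.888 and also run 0.70 to 0.95.

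**4. Where each quantity reaches 50% at t = 0.888.** The 50% cut is illustrative; it is not in the SAP.

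- Design effect: z = (1.960 − 2.82 × 0.112)/√0.888 = 1.745, two-sided p = 0.081.
- Observed effect and PP: z = 1.960 × √0.888 = 1.847, p = 0.065.

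**5. Values for non-significant results at t = 0.888.**

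| Two-sided p | CP, design effect | CP, observed effect | PP, flat prior |
|---|---|---|---|
| 0.051 | 72% | 63% | 62% |
| 0.06 | 65% | 54% | 54% |
| 0.08 | 51% | 38% | 39% |
| 0.10 | 39% | 26% | 27% |

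**6. Dependence on t and on the threshold.** Entries are the largest p that reaches the threshold.

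| t | 50%, design | 50%, observed or PP | 80%, design | 80%, observed | 80%, PP |
|---|---|---|---|---|---|
| 0.70 | 0.183 | 0.101 | 0.060 | 0.043 | 0.036 |
| 0.888 | 0.081 | 0.065 | 0.041 | 0.035 | 0.033 |
| 0.95 | 0.062 | 0.056 | 0.039 | 0.036 | 0.036 |

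**7. Error rate if a 50% reading were used as a success rule at t = 0.888.** The upper tail beyond z = 1.745 is 4.0%, and beyond z = 1.847 it is 3.2%, against the nominal 2.5% per side.

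**The case against.** The strongest defence is that Section 8 already settles the matter. Conditional power and predictive probability fall under "All other statistical results are to be regarded as exploratory". They sit under a heading separate from the primary analysis, and in 14.1.1 the log-rank test is the only between-group test named. To support a decision is not to override it. The additions are disclosed in Section 18, the SAP is to be signed before code release, and the trial is phase IIa. Reporting both assumed effects limits selective use of the favourable one, and the figures may equally show that the shortfall does not explain a negative result.

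Much of this stands. The sections can be reconciled by letting Section 8 govern, and a descriptive account of what the shortfall cost is legitimate. Two objections to the arithmetic also stand. The 50% cut appears nowhere in the SAP. And 0.888 is a ratio of randomised patients, whereas log-rank information depends on events in the Full Analysis Set, which is limited to patients with successful cardioversion and whose size the SAP does not give.

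What does not stand is that no change is needed. The sentence in 14.1.3 names the statistical decision as the purpose of these figures, and does not refer back to Section 8.

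A reader might go further and infer that the plan raises the false-positive rate above 5%, or that it is built to present a failed trial as positive. The document supports neither reading. It attaches no success rule to these quantities, keeps the two-sided 5% level, and shows no such intent.

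**Conclusion.** The point holds as a tension between two sections, with a conditional consequence. Section 14.1.3 assigns a role in the decision to quantities that Section 8 makes exploratory and that carry no information beyond the final test statistic. The formal type I error is unchanged if Section 8 governs.

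If the figures did inform the conclusion, the room for a near miss would depend on choices the SAP leaves open. Under a 50% reading it extends to p = 0.081 (design effect) or p = 0.065 (observed effect or flat-prior predictive probability) at t = 0.888. Over t from 0.70 to 0.95 these limits run from 0.18 to 0.06 and from 0.10 to 0.056. Under an 80% reading at t = 0.888 there is no room at all; at t = 0.70 only the design-effect version passes p = 0.05, and it stops at about 0.060.

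These figures assume the Brownian-motion approximation, a final critical value of 1.96, a design drift of 2.82 and, for the predictive probability, a flat prior. The point is worth correcting: the remedy is specific and cheap, and it fixes in advance what a near miss can be claimed to show.

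**What to change.** In Section 14.1.3, replace the clause that links these quantities to the statistical decision. Suggested wording: *Predictive probability and conditional power are descriptive only. The conclusion on the primary criterion rests solely on the log-rank test at the two-sided 5% level (Section 8).* If the calculations are kept, also state the prior and the information scale, preferably events in the Full Analysis Set. Use the hazard ratio and 95% CI already planned in 14.1.1 to express the uncertainty left by the smaller sample.

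The cost is a sentence or two in the SAP before code release, with no change to data or design. The downside for the sponsor is that it cannot use these figures to argue for a near miss.

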#### 14.1.4. Sensitivity Analyses

Primary analysis of the main criterion (see section 14.1.1) will be conducted on the subgroups of patients defined as:

- FAS patients with a DHA baseline  $\leq$  median of the DHA at baseline
- FAS patients with a DHA baseline  $>$  median of the DHA at baseline

*Note:* The medians separating subgroups will be calculated on the FAS.

- FAS patients with vascular or cardiac therapeutic procedures identified in the data review meeting report
- FAS patients without vascular or cardiac therapeutic procedures identified in the data review meeting report

Other Cox models will be used to investigate the influence of Treatment \* country, Treatment \* Baseline interactions (DHA baseline), and to evaluate the influence of some prognostic or demographic factors (gender, age, BSA), baseline characteristics of the disease (duration of current AF up to selection visit, time from first documented persistent AF up to selection visit, Time from heart failure diagnosis up to selection visit, NYHA grade, left atrial area, Left ventricular ejection fraction on the Full Analysis Set.

ROC curves will be also constructed according to DHA and time to first recurrence thresholds (for example, positive/negative DHA vs first recurrence  $\leq\geq$  1 week).

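### The primary analysis is repeated separately in patients with and without vascular or cardiac procedures, but no treatment-by-procedure interaction is planned, so nothing tests whether the effect differs between them

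*SAP*

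**What the plan says.** Section 14.1.4 of the SAP introduces four subgroups with the words "Primary analysis of the main criterion (see section 14.1.1) will be conducted on the subgroups of patients defined as". Two are formed by the median of baseline DHA. The other two are patients in the Full Analysis Set (FAS) with procedures and their complement, "FAS patients without vascular or cardiac therapeutic procedures identified in the data review meeting report". The analysis being repeated, in section 14.1.1, consists of Kaplan-Meier curves, a log-rank test and a Cox HR with a Wald 95% CI. Appendix 5 accordingly lists, for each procedure subgroup, a survival-curve and log-rank output, a Kaplan-Meier summary and a Cox output.

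The same section continues: "Other Cox models will be used to investigate the influence of Treatment" by country and by baseline DHA, and then names single prognostic factors. Appendix 5 has interaction tables for country and DHA only. Procedure status appears in none of these Cox models, either as an interaction or as a factor.

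Section 8 reserves causal interpretation for the primary test and makes everything else exploratory. Section 18 records that the subgroup analyses were added after the protocol.

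**The concern.** Dividing patients by procedure status asks whether the drug works differently in the two groups. For DHA the plan provides a model that addresses that question. For procedures it provides two separate results and no comparison between them. A significant log-rank test in one subgroup and a non-significant one in the other is not evidence that the effects differ: each subgroup holds only part of the events, so one can easily miss significance while the true effect is the same in both.

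At stake is a sentence in the study report saying that the effect was seen only in patients without procedures, or only in those with them. In a phase IIa trial, such a sentence could shape the population chosen for a later study.

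**Working it through.** **Inputs from the SAP's sample size section**
- Event rates: "Assuming an AF recurrence rate of 85% under placebo and 65% under active group".
- Test: "using a log-rank test of survival curves with a 80 % power and a 5 % two-sided significance level".
- Size: "a sample size of 64 assessable patients per group is" required, and after the 15% allowance "a minimum of 76 patients have to be randomised per group".
- 135 patients were actually randomised.

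**Reproducing the plan's figure**
- HR = ln(0.35)/ln(0.15) = 0.553.
- Freedman events: (1.960 + 0.842)² × [(1 + 0.553)/(1 − 0.553)]² = 94.9, so 95.
- Mean event rate (0.85 + 0.65)/2 = 0.75. Per group: 95/0.75/2 = 63.3, so 64. This matches.
- 64/0.85 = 75.3, so 76. This matches.

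**Assumptions, not given in the SAP**
- FAS size: 135 × 0.85 = 114.75, about 115. The actual number depends on how many patients were successfully cardioverted.
- Events: 114.75 × 0.75 = 86. For simplicity this is held at 86 when the HR is varied.
- Share of patients with procedures: range 10% to 50%.
- The same true HR in both subgroups.

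**Chance that exactly one subgroup is significant**

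Freedman power with E events is Φ(√E × (1 − HR)/(1 + HR) − 1.960). If p1 and p2 are the two subgroup powers, the chance of exactly one significant result is p1(1 − p2) + p2(1 − p1). At HR 0.553:

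| Split | Power, smaller | Power, larger | Exactly one p<0.05, formula | Exactly one p<0.05, simulation |
|---|---|---|---|---|
| 50/50 | 47% | 47% | 50% | 50% |
| 30/70 | 31% | 61% | 54% | 55% |
| 20/80 | 22% | 67% | 59% | 60% |
| 10/90 | 13% | 72% | 66% | 66% |

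The simulation used 115 patients, exponential times and 10,000 runs per split. At 50/50 the formula gives both significant in 22% and neither in 28%. If all 135 patients were assessable (135 × 0.75 = 101 events), exactly one is significant in 50% to 70% across the same splits.

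**Smaller true effects, 86 events, splits 50/50 to 10/90**

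Here Schoenfeld power is used, Φ(√E × |ln HR|/2 − 1.960), with the opposite tail added. Exactly one subgroup is significant in about 34-37% at HR 0.70, about 20% at HR 0.80 and about 12% at HR 0.90. With no effect at all, at least one of two 5% tests is significant in 1 − 0.95² = 9.75%.

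A valid 5% interaction test would wrongly signal a difference in about 5% of trials in any of these settings.

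**What the interaction test could detect**

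The standard error of the difference in log HR is √(4/E1 + 4/E2). With 86 events it is 0.431 at 50/50, 0.539 at 20/80 and 0.719 at 10/90. Power to detect a two-fold ratio of HRs, Φ(ln 2/SE − 1.960), is 36%, 25% and 16%.

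**The case against.** The strongest reply is that the plan already contains most of what is needed. Each procedure subgroup gets an HR with its CI. The subgroups do not overlap, so a reader can form an approximate test of the difference by hand. Section 8 already rules out a causal reading. All of this stands, and it limits how serious the point is. What it does not supply is a planned test or estimate of the difference, which the SAP does provide for DHA.

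Three stronger readings are tempting, and the document does not support them.
- A reader might infer that the procedure subgroups can be compared only by setting one p-value against the other. The planned HRs and CIs show otherwise.
- A reader might infer that all four subgroups lack an interaction. The DHA pair has one; the gap is the procedure pair alone.
- A reader might infer that a one-subgroup finding would usually be chance. The calculation gives the probability of discordant p-values when the effects are equal. It does not give the probability that the effects are equal once discordance is seen.

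It is also fair to object that the 50-66% needs the full design effect; the figure is much lower for weaker effects. The proposed model has its own limits too. Its power is poor. Section 14.1.4 leaves the procedures to the data review meeting report and does not say whether they precede randomisation. If later procedures count, procedure status could itself be affected by treatment.

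The section's title is a minor matter. Section 18 already calls these subgroup analyses, and excluding patients with procedures can also serve as a robustness check.

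**Conclusion.** The point holds in a narrow form: one interaction term is missing for one pair of exploratory subgroups. Without it, the separate log-rank results can mislead. With the same true effect in both subgroups, they disagree on significance in about half to two thirds of trials at the design HR, about a third at HR 0.70 and about a fifth at HR 0.80. These figures rest on an assumed FAS of about 115, about 86 events and an assumed procedure share of 10% to 50%. The primary analysis and its conclusion are unaffected.

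**What to change.** - Add to section 14.1.4 one Cox model with treatment, procedure status (yes/no) and their interaction, alongside the DHA model, and list one matching output in Appendix 5.
- State that any claim of an effect differing by procedure status will rest on the interaction estimate with its CI, and not on the separate log-rank p-values.
- State that the interaction test has low power, so a non-significant result does not show that the effects are equal.
- Say whether procedures after randomisation are counted. If they are, state that neither the subgroup results nor the interaction can be read as clean effect modification.

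Optional: retitle the section as subgroup analyses, and drop the log-rank p-values in all four subgroups while keeping the HRs, CIs and curves.

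The cost is one extra model, one table and a few sentences. No new data are needed.
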